Appendix 5. Algorithm for Calculating CPDAI and mCPDAI

CPDAI is a validated composite instrument to assess psoriatic disease activity and response to therapy (Mumtaz et al. 2011). This instrument assesses individual domains:

- peripheral arthritis as assessed by the number of tender and swollen joints and the HAQ-DI
- skin as assessed by the PASI and the DLQI
- enthesitis as assessed by the number of sites with enthesitis and the HAQ-DI
- dactylitis as assessed by the number of digits affected and the HAQ-DI
- spinal disease as assessed by the BASDAI and ASQoL.

The table below shows the instruments for each domain and the range in their total score:

Domain	Instrument	Total Score Range
Peripheral arthritis	TJC/SJC	0-68/0-66
	HAQ-DI	0-3
Skin disease	PASI	0-72
	DLQI	0-30
Enthesitis	LEI	0-6
	HAQ-DI	0-3
Dactylitis	Digit Score	0-20
	HAQ-DI	0-3
Spinal disease	BASDAI	0-10
	ASQoL	0-18

Each domain is scored from 0–3. Individual domain scores are summed to give an overall composite CPDAI score. The composite scores range from 0 to 15 for the assessment, with a higher score indicating higher disease activity. See the table below for details:

Domain	Not involved (0)	Mild (1)	Moderate (2)	Severe (3)
Peripheral arthritis	TJC and SJC = 0	TJC or SJC \leq 4; and HAQ-DI \leq 0.5	TJC or SJC \leq 4 and HAQ-DI $>$ 0.5; or TJC or SJC $>$ 4 and HAQ-DI \leq 0.5	TJC or SJC $>$ 4 and HAQ-DI $>$ 0.5
Skin disease	Absence of plaque psoriasis as defined by the eCRF or PASI = 0	PASI \leq 10 and DLQI \leq 10	PASI \leq 10 and DLQI $>$ 10; or PASI $>$ 10 and DLQI \leq 10	PASI $>$ 10 and DLQI $>$ 10
Enthesitis	Absence of enthesitis as defined by the eCRF	LEI \leq 3 sites; HAQ-DI \leq 0.5	LEI \leq 3 sites and HAQ-DI $>$ 0.5; or LEI $>$ 3 sites and HAQ-DI \leq 0.5	LEI $>$ 3 and HAQ-DI $>$ 0.5
Dactylitis	Absence of dactylitis as defined by the eCRF	Digit score \leq 3 digits; HAQ-DI \leq 0.5	Digit score \leq 3 and HAQ-DI $>$ 0.5; or Digit score $>$ 3 and HAQ-DI \leq 0.5	Digit score $>$ 3 and HAQ-DI $>$ 0.5
Spinal disease	BASDAI = 0 and ASQoL = 0	BASDAI $<$ 4; ASQoL $<$ 6	BASDAI $<$ 4 and ASQoL \geq 6; or BASDAI \geq 4 and ASQoL $<$ 6	BASDAI $>$ 4 and ASQoL \geq 6

The modified CPDAI will sum up each domain with the exception of spinal disease score (0–3). The composite scores range from 0 to 12 for the assessment, with a higher score indicating higher disease activity.

Appendix 6. Deviation of SF-36v2® Health Survey, Acute Version Scores

The SF-36v2® Health Survey Scoring Software (QualityMetric Health Outcomes™ Scoring Software 4.5) will be used to calculate the SF-36v2® 8-domain and 2-component summary scores (Saris-Baglama et al. 2004). The SF-36 is a 36-item, patient-completed measure designed to be a short, multipurpose assessment of health in the areas of physical functioning, role-physical, role-emotional, bodily pain, vitality, social functioning, mental health, and general health. The 2 overarching dimensions of mental well-being and physical well-being are captured by the Physical Component Summary (PCS) and Mental Component Summary (MCS) scores, respectively. The summary scores range from 0 to 100, with higher scores indicating better levels of function and/or better health. Items are answered on Likert scales of varying lengths. In this study, the SF-36 acute version will be used, which has a 1-week recall period (The SF Community – SF-36 Health Survey Update [WWW]).

The Scoring Software performs a 4-step process to calculate raw domain scores and t-scores consisting of

1. Data Cleaning and Item recording: First, data are checked for out of range values, converting invalid items to missing values. Next, items (BP01, BP02, GH01, GH03, GH05, VT01, VT02, SF01, MH03, MH05) are reverse scored, so that higher scores denote better health for all SF-36 items.
2. Although current research indicates a linear relationship between the SF-36 items and the underlying health concept, empirical research suggests that items GH01 and BP01 require recalibration to satisfy important scaling assumptions. Item GH01 will be rescored according to the following table:

Response to GH01	Recommended Value / Recalibrated Value
Excellent	5.0
Very Good	4.4
Good	3.4
Fair	2.0
Poor	1.0

The BP01 will be rescored with

Response Choices	Final Item Value
None	6.0
Very mild	5.4
Mild	4.2
Moderate	3.1
Severe	2.2
Very severe	1.0

Item 08 (BP02) will be rescored if BP01 and BP02 were answered

Response Choices	If BP02 Pre-coded Item Value	and BP01 Pre-coded Item Value	Then Final Item 08 (BP02) Value
Not at all	1	1	6
Not at all	1	2-6	5
A little bit	2	1-6	4
Moderately	3	1-6	3
Quite a bit	4	1-6	2
Extremely	5	1-6	1

Scoring of BP02 if BP01 is not answered:

Response Choices	Final Item Value
Not at all	6.0
A little bit	4.75
Moderately	3.5
Quite a bit	2.25
Extremely	1.0

3. After this rescoring, the raw domain scores will be calculated for the scale. Domain scores are the simple algebraic sum of the final values for all items in that scale.
4. All raw domain scores will be transformed to a 0-100 scale, with 0 being the lowest and 100 the highest possible score.
5. Finally, the 0-100 scores will be transformed to t-score based scores. First, a z-score transformation using the mean for the respective recall period, here 1 week recall, of the 2009 general U.S. population will be used. Then the distribution of z-score is linearly transformed to have a mean of 50 and a SD of 10 by multiplying each z-score with 10 and adding 50.

The calculation of component scores is a 3-step process using the domain scores, calculated as described above:

1. The standardized scores from Step 5, depending on the chosen recall period, are calculated.
2. These standardized Physical and Mental component scores are calculated as the weighted sums by the factor score coefficients, derived from the 1990 general U.S. population, with the domain scores. If any domain score is missing then the aggregate Physical or Mental score will not be calculated.
3. The PCS and MCS are linearly transformed by multiplying by 10 and adding 50 to obtain the aggregate t-score based scoring.

To run the scoring algorithm, the SF-36 items recorded in the study database will be exported into a comma- or tab-separated values file (*.csv, *.tab). This file will then be loaded into the

Scoring Software to perform the calculations described above. The resulting raw domain scores and t-scores (domain scores) will then be exported into a comma- or tab-separated values file and imported into SAS for storage in the SDTM/ADaM datasets.

The comma- or tab-separated values file, each row will be one patient record and the first row will comprise the header columns, will have the following column specification: (to comply with the Scoring Software requirements)

eCRF Row #	Column label for export to comma- or tab-separated values file [*.csv, *.tab]	Annotated SF-36 eCRF Variable [Format: SF36V2RXX_SF36V2F1]	Item Number, Score range	eCRF question / Specification
1	GH01	[SF36V2R01_SF36V2F1]	Item # 1, Range 1-5	In general, would you say your health is:
2	HT	[SF36V2R02_SF36V2F1]	Item # 2, Range 1-5	Compared to one week ago, how would you rate your health in general now?
3	PF01	[SF36V2R03_SF36V2F1]	Item # 3a, Range 1-3	Vigorous activities, such as running, lifting heavy objects, participating in strenuous sports
4	PF02	[SF36V2R04_SF36V2F1]	Item # 3b, Range 1-3	Moderate activities, such as moving a table, pushing a vacuum cleaner, bowling, or playing golf
5	PF03	[SF36V2R05_SF36V2F1]	Item # 3c, Range 1-3	Lifting or carrying groceries
6	PF04	[SF36V2R06_SF36V2F1]	Item # 3d, Range 1-3	Climbing several flights of stairs
7	PF05	[SF36V2R07_SF36V2F1]	Item # 3e, Range 1-3	Climbing one flight of stairs
8	PF06	[SF36V2R08_SF36V2F1]	Item # 3f, Range 1-3	Bending, kneeling, or stooping
9	PF07	[SF36V2R09_SF36V2F1]	Item # 3g, Range 1-3	Walking more than a mile
10	PF08	[SF36V2R10_SF36V2F1]	Item # 3h, Range 1-3	Walking several hundred yards
11	PF09	[SF36V2R11_SF36V2F1]	Item # 3i, Range 1-3	Walking one hundred yards
12	PF10	[SF36V2R12_SF36V2F1]	Item # 3j, Range 1-3	Bathing or dressing yourself
13	RP01	[SF36V2R13_SF36V2F1]	Item # 4a, Range 1-5	Cut down the amount of time you spent on work or other activities
14	RP02	[SF36V2R14_SF36V2F1]	Item # 4b, Range 1-5	Accomplished less than you would like
15	RP03	[SF36V2R15_SF36V2F1]	Item # 4c, Range 1-5	Were limited in the kind of work or other activities
16	RP04	[SF36V2R16_SF36V2F1]	Item # 4d, Range 1-5	Had difficulty performing the work or other activities (for example, it

eCRF Row #	Column label for export to comma- or tab-separated values file [*.csv, *.tab]	Annotated SF-36 eCRF Variable [Format: SF36V2RXX_SF36V2F1]	Item Number, Score range	eCRF question / Specification
				took extra effort)
17	RE01	[SF36V2R17_SF36V2F1]	Item # 5a, Range 1-5	Cut down the amount of time you spent on work or other activities
18	RE02	[SF36V2R18_SF36V2F1]	Item # 5b, Range 1-5	Accomplished less than you would like
19	RE03	[SF36V2R19_SF36V2F1]	Item # 5c, Range 1-5	Did work or other activities less carefully than usual
20	SF01	[SF36V2R20_SF36V2F1]	Item # 6, Range 1-5	During the past week, to what extent has your physical health or emotional problems interfered with your normal social activities with family, friends, neighbors, or groups?
21	BP01	[SF36V2R21_SF36V2F1]	Item # 7, Range 1-6	How much bodily pain have you had during the past week?
22	BP02	[SF36V2R22_SF36V2F1]	Item # 8, Range 1-5	During the past week, how much did pain interfere with your normal work (including both work outside the home and housework)?
23	VT01	[SF36V2R23_SF36V2F1]	Item # 9a, Range 1-5	Did you feel full of life?
24	MH01	[SF36V2R24_SF36V2F1]	Item # 9b, Range 1-5	Have you been very nervous?
25	MH02	[SF36V2R25_SF36V2F1]	Item # 9c, Range 1-5	Have you felt so down in the dumps that nothing could cheer you up?
26	MH03	[SF36V2R26_SF36V2F1]	Item # 9d, Range 1-5	Have you felt calm and peaceful?
27	VT02	[SF36V2R27_SF36V2F1]	Item # 9e, Range 1-5	Did you have a lot of energy?
28	MH04	[SF36V2R28_SF36V2F1]	Item # 9f, Range 1-5	Have you felt downhearted and depressed?
29	VT03	[SF36V2R29_SF36V2F1]	Item # 9g, Range 1-5	Did you feel worn out?
30	MH05	[SF36V2R30_SF36V2F1]	Item # 9h, Range 1-5	Have you been happy?
31	VT04	[SF36V2R31_SF36V2F1]	Item # 9i, Range 1-5	Did you feel tired?
32	SF02	[SF36V2R32_SF36V2F1]	Item # 10, Range 1-5	During the past week, how much of the time has your physical health or emotional problems interfered with your social activities (like visiting with friends, relatives, etc.)?
33	GH02	[SF36V2R33_SF36V2F1]	Item # 11a, Range 1-5	I seem to get sick a little easier than other people

eCRF Row #	Column label for export to comma- or tab-separated values file [*.csv, *.tab]	Annotated SF-36 eCRF Variable [Format: SF36V2RXX_SF36V2F1]	Item Number, Score range	eCRF question / Specification
34	GH03	[SF36V2R34_SF36V2F1]	Item # 11b, Range 1-5	I am as healthy as anybody I know
35	GH04	[SF36V2R35_SF36V2F1]	Item # 11c, Range 1-5	I expect my health to get worse
36	GH05	[SF36V2R36_SF36V2F1]	Item # 11d, Range 1-5	My health is excellent
	SUBJID			Subjects ID
	VISID			Visid ID
	Sex			Sex coded as: f/m
	DateOfBirth			Date of birth formatted as: mm/dd/yyyy (when scoring software is run in US), or dd/mm/yyyy (when scoring software is run in non-US)
	RecordID			Running number for the exported records

The SF-36 Scoring Software will derive raw domain scores and t-scores that can be exported into a comma- or tab-separated values file (*.csv, *.tab) with the following columns added:

Column label added to comma- or tab-separated values file from export [*.csv, *.tab]	Scoring Software specification
PF	Physical Functioning domain score
RP	Role Limitations Due To Physical Health domain score
BP	Bodily Pain domain score
GH	General Health Perceptions domain score
VT	Vitality domain score
SF	Social Functioning domain score
RE	Role Limitations Due To Emotional Problems domain score
MH	Mental Health domain score
PCS	Physical Component score
MCS	Mental health Component score

For scoring the trial data, the Missing Data Estimator option will not be selected. If an item is missing, there will be no imputation conducted by the Scoring Software. Only complete questionnaire data will be scored.

The Scoring Software also allows for calculating domain and component scores from weights derived from a oblique factor solution for comparative purposes. This option will not be used.

The SF-36 scoring using the Scoring Software will be conducted by a 2 person team overseeing each other in a single scoring session. In case of relevant observations during the scoring, those will be documented in pertinent meeting minutes and filed as part of the study documentation.

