Medical Outcomes Study 36-item Short Form Health Survey (SF-36)	A 36-item patient-administered measure designed to be a short, multipurpose assessment of health in the areas of physical functioning, role-physical, role-emotional, bodily pain, vitality, social functioning, mental health, and general health. The 2 overarching domains of mental well-being and physical well-being are captured by the Mental Component Summary (MCS) and Physical Component Summary (PCS) scores.	Observed and change from baseline in: 8 associated domain scores: 
 Physical Functioning Role Physical Bodily Pain General Health Vitality Social Functioning Role Emotional Mental Health 	Per copyright owner, the Quality Metric Health Outcomes™ Scoring Software 4.5 will be used to derive SF-36 domain and component scores. After data quality-controls, the SF-36 software will re-calibrate the item-level responses for calculation of the domain and component scores. These raw scores will be transformed into the domain scores (t-scores)	Missing data handling offered by SF-36 software will not be used

Measure	Description	Variable	Derivation/Comment	Imputation Approach if with Missing Components
	
Items are answered on Likert scales of varying lengths. The SF-36 version 2 (acute version) health survey will be used, which has a 1-week recall period (Brazier et al. 1992; Ware and Sherbourne 1992).
	
2 component Scores:
 
 • MCS Score • PCS Score 	
using the 1-week recall period. The procedure to derive the SF-36 scores is described in Appendix 6. The summary scores range from 0 to 100. It entails exporting the patient data in a CSV or tab-delimited file for import, generation of the SF-36 scores and reports, and export of the calculated scores in a CSV or tab-delimited file for integration into SDTM/ADaM datasets. The summary scores range from 0 to 100.
	

Measure	Description	Variable	Derivation/Comment	Imputation Approach if with Missing Components

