		DLQI work and school domain	Sum of responses of questions #7A and #7B: #7A. Has your skin prevented you from working or studying? #7B. If No: how much has your skin been a problem at work or studying?	If the answer to question #7A is missing, this domain is missing. If #7A is No, and #7B is missing, this domain is missing.
		DLQI personal and relationships domain	Sum of responses of questions #8 and #9: #8. How much has your skin created problems with your partner or any of your close friends or relatives? #9. How much has your skin caused any sexual difficulties?	If 1 question in a domain is missing, that domain is missing.
		DLQI treatment	Response of question #10: #10. How much of a problem	If 1 question in a domain is missing, that domain is

Measure	Description	Variable	Derivation/Comment	Imputation Approach if with Missing Components
			has the treatment for your skin been, for example by making your home messy, or by taking up time?	missing.
		DLQI total score	A DLQI total score is calculated by summing all 10 question responses and has a range of 0 to 30 (less to more impairment) (Finlay and Khan 1994; Basra et al. 2008).	If 2 or more questions are missing, the total score is missing. Note: #7B could be a valid missing while #7A is not “No.” That is, #7 should be considered as 1 question.
		Change from baseline in DLQI total score	Calculated as observed DLQI – baseline DLQI	Missing if baseline or observed value are missing
		DLQI (0,1)	A DLQI (0,1) response is defined as a post-baseline DLQI total score of 0 or 1. A DLQI total score of 0 to 1 is considered as having no effect on a patient’s HRQoL (Khilji et al. 2002; Hongbo et al. 2005).	Missing if DLQI total score is missing
Treatment Satisfaction Questionnaire (TSQ)	The TSQ is a clinician-administered questionnaire that provides an assessment of the patient’s opinion of the effectiveness, safety, and overall satisfaction of the study medication. Patients will be asked to respond to questionnaire items using a 4-point	Question #1 = “mostly satisfied”	Patient’s answer to Question #1: Please tell me whether you are mostly satisfied, somewhat satisfied, somewhat dissatisfied, or mostly dissatisfied with the effectiveness of this medication is mostly satisfied.	Single item, missing if missing

Measure	Description	Variable	Derivation/Comment	Imputation Approach if with Missing Components

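### Read literally, the SF-36 completeness rule lets one blank item void all ten scores; the avoidable loss falls mainly on the eight exploratory domain scores

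*SAP*

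**What the plan says.** SAP Appendix 6 switches off the software's Missing Data Estimator for the trial data. It then adds two sentences: "If an item is missing, there will be no imputation conducted by the Scoring Software" and "Only complete questionnaire data will be scored". Table RHCF.6.5 in SAP Section 6.13 states only the first of these restrictions: "Missing data handling offered by SF-36 software will not be used".

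The same appendix also describes what happens below the level of the whole form:

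- Cleaning: "First, data are checked for out of range values, converting invalid items to missing values".
- Pain items: a separate value table headed "Scoring of BP02 if BP01 is not answered".
- Domains: "Domain scores are the simple algebraic sum of the final values for all items in that scale".
- Summary scores: "If any domain score is missing then the aggregate Physical or Mental score will not be calculated".

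The export table in Appendix 6 lists HT, the comparison with one week ago, as its second row. The output table lists ten scores (PF, RP, BP, GH, VT, SF, RE, MH, PCS, MCS). HT belongs to none of them.

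Table RHCF.6.6 classes PCS and MCS as secondary analyses and the eight domain scores as exploratory, all at Weeks 4, 12, 16, 24, 32 and 52.

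**The concern.** The completeness sentence takes the questionnaire as its unit, while the rest of Appendix 6 works by item and by domain. If a form with any blank is not scored, the BP02 table for an unanswered BP01 can never be used. Nor can the rule on a missing domain, because no record would have some domains present and others absent.

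Two programmers could handle an incomplete form differently and each point to the SAP. One would leave the record unscored. The other would keep every domain whose items are all answered.

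At stake are valid domain answers discarded because of a blank elsewhere on the form. In the case of HT, the blank is in an item that no score uses. A blank at baseline matters most. The Protocol schedule has a single SF-36 before treatment (Week 0), and SAP Section 6.1 does not calculate change when the baseline is missing. The affected scores then drop out of all six visits for that patient.

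**Working it through.** The plan states no figure for this point, so the check compares two readings of Appendix 6.

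**Inputs from the SAP.** Items per domain, counted from the Appendix 6 export table: PF 10, RP 4, BP 2, GH 5, VT 4, SF 2, RE 3, MH 5. Sum: 10 + 4 + 2 + 5 + 4 + 2 + 3 + 5 = 35. Adding HT gives 36, which matches the stated length of the questionnaire.

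**Assumed input.** Each item is blank independently with probability q. The documents give no value for q; the range shown is 0.05% to 0.5%.

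**One blank item, no probability needed.**

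| Blank item | Whole-form rule | Domain-level rules, no imputation |
|---|---|---|
| Any of the 35 scale items | 10 of 10 scores lost | 3 of 10 lost (own domain, PCS, MCS) |
| HT | 10 of 10 lost | 0 of 10 lost |

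Averaged over a randomly placed single blank, the loss is 10 scores against (35 × 3 + 1 × 0)/36 = 2.9.

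**Availability as a function of q.**

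- Whole-form rule, every score: (1−q)^36.
- Domain-level rules, PCS and MCS: (1−q)^35, since every scale item is needed.
- Domain-level rules, a domain of k items: (1−q)^k, averaged over the eight domains.
- Extra PCS/MCS loss from the completeness sentence: (1−q)^35 − (1−q)^36 = q(1−q)^35.

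| Assumed q | All scores, whole-form | PCS/MCS, domain-level | PCS/MCS gain (points) | Mean domain, domain-level | Mean domain gain (points) |
|---|---|---|---|---|---|
| 0.05% | 98.22% | 98.26% | 0.05 | 99.78% | 1.57 |
| 0.1% | 96.46% | 96.56% | 0.10 | 99.56% | 3.10 |
| 0.2% | 93.05% | 93.23% | 0.19 | 99.13% | 6.08 |
| 0.5% | 83.49% | 83.91% | 0.42 | 97.84% | 14.35 |

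Gains are computed before rounding. For scale, if all 550 randomized patients complete a baseline form and q is 0.1%, the whole-form rule leaves about 19.5 forms unscored. Domain-level scoring leaves about 18.9 without PCS and MCS, and on average about 2.4 without a given domain.

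**The case against.** The sponsor has several fair replies.

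1. **PCS and MCS are hardly touched.** A reader might infer that the sentence needlessly deletes secondary-endpoint data on a large scale. The documents do not support that. A domain sums all its items, nothing is imputed, and a missing domain already blocks both summary scores. A blank in any of the 35 scale items therefore removes PCS and MCS whether or not the completeness sentence is there. BP01 is arguable only if the BP02 table is taken to allow a pain score without it. This reply stands, and it confines the PCS/MCS effect to HT.

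2. **The passages need not contradict each other.** The item and domain steps are introduced as what the scoring software does, while the completeness sentence belongs to a paragraph on scoring the trial data. It can be read as a stricter trial-specific override. That makes the missing-domain rule redundant rather than contradictory. The BP02 table fits less easily, though it too may be a general description of the software. This reply stands against calling it an outright contradiction. It does not explain why HT should count.

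3. **The sentence may only restate the ban on imputation.** It follows that ban directly, and Appendix 6 describes no step that removes incomplete records before export. This is possible, but then the wording says more than is meant and should still be changed.

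4. **Complete-item scoring is common in this SAP.** PASI, LEI, SPARCC, LDI-B, DAS28-CRP, mCPDAI and the EQ-5D index all become missing if a component is missing. HAQ-DI, NAPSI, joint counts and the DLQI total are more tolerant; for the last, "If 2 or more questions are missing, the total score is missing". SF-36 is not an outlier in refusing imputation, and declining the estimator is a deliberate choice stated twice. This stands. What is unusual is letting an unused item, or an item of another domain, void a complete domain.

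5. **Blanks may be rare.** Protocol Section 9 has this questionnaire completed electronically, and Protocol Appendix 3.2.1 describes tablet entry. The documents do not say whether items can be skipped, so this limits the size without settling it.

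**Conclusion.** The point holds as a minor, low-cost improvement. Read literally, the completeness sentence costs ten of ten scores for any blank item, where the appendix's own domain-level rules would cost three for a scale item and none for HT. The avoidable loss lies mainly in the eight exploratory domain scores: a mean of 1.57 to 14.35 percentage points at assumed independent blank rates of 0.05% to 0.5% per item. For PCS and MCS it is about 0.05 to 0.42 points over the same range, arising only when HT alone is blank.

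The single-blank counts follow from the SAP. The percentages rest on assumed rates and on independence, and they shrink to near zero if the tablet forces an answer to every item. A reader might also infer bias from sicker patients skipping items, but nothing in the documents bears on who skips items. The primary and major secondary endpoints do not use the SF-36 and are unaffected.

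**What to change.** In SAP Appendix 6, replace the completeness sentence with: *Each domain is scored when all its own items are valid; PCS and MCS are calculated when all 8 domains are scored; the HT item is not required.*

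State as well whether the BP02 table for an unanswered BP01 applies. If every item of a domain must be valid, that table cannot rescue the pain score and should be marked as general software description. If it is meant to apply, the pain domain needs an explicit exception.

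The cost is one replaced sentence and one clarification. The ban on imputation stays, and the Missing Data Estimator is not needed.
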